Collaborative-Care Rehabilitation to Improve Functional Outcomes after Dysvascular Amputation

Statistical Analysis Plan
Version Date: 01.05.2014

Between-group differences in all outcomes at 12- and 24-week tests will be evaluated using maximum likelihood estimation in a multivariate repeated measures model. The maximum likelihood method uses all available data and provides unbiased estimates under the assumption that missing data are missing at random. The model for each outcome will be controlled for baseline value of the outcome, rehabilitation clinic site (VA/non-VA), diagnosis of DM, and diagnosis of PAD. Estimated group means and within-group mean changes over time for each outcome will be reported with 95% confidence intervals. This early phase study is powered for one endpoint; multiple secondary endpoints are reported to guide further research without adjustment for multiplicity.

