D5. Data Analysis. Data will be managed using REDCap (Research Electronic Data Capture; which is HIPAA compliant).⁶⁸ Primary analysis will be group differences in TUG times (primary outcome) at the 12-week time point. As a pilot feasibility study, data will only be analyzed for participants with sufficient intervention exposure, defined as six weeks. For participants who withdraw at or beyond six weeks of intervention, an early termination test will be performed and carried forward as the end-point. Participants who withdraw before completing six weeks will be lost to follow-up and no imputation will be performed for missing data. Attempts will be made to test all participants at 24-weeks. However, missing 24-week data will not be imputed from the 12 week measurement, as this would bias the effect following the primary end-point (i.e., it is expected that both groups would have worse 24- compared to 12-week outcomes). Group differences will be based on a linear model with TUG as the outcome and explanatory variables being primary medical diagnosis (PAD, DM, or both), rehabilitation site, treatment group, and baseline TUG. Group differences will be determined by this single test to protect against Type I error (α level: 0.05).

Secondary analyses will include differences at 12-weeks in the other outcomes (2MW, 5mW, PEQ-MS 12/5, Houghton Scale, PSFS, Activity level, number of healthcare provider visits, and number of hospital encounters) using the same method as for the primary outcome. A mixed-effects model with time as a fixed covariate across baseline, 12-, and 24-weeks will be used to evaluate long-term outcomes (24-week) and make inferences regarding the effectiveness of the intervention up to 12-weeks after intervention is complete. As with the other analyses, evaluation of the time trajectory will be conditioned on stratification variables and baseline values of the outcome measure. Also the mixed-effects model will not include data from subjects who drop prior to 6 weeks.

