The exploratory aim of identifying predictors of physical activity and disability will be analyzed by regression analysis. First, variables will be grouped into demographic/anthropometric, activity/mobility, health behaviors, physical health, amputated-limb health, contralateral-limb health, and cognitive/affective health, and healthcare use factors. A hierarchical process will be used to screen variables within each group of factors to identify the best predictors within each group. Finally, the best predictor variables from each group will be entered into a regression model to determine models containing subsets of the variables that predict the outcome, based on R^2_{adj} . The most parsimonious model will be identified by comparing the 10 best models, using partial F-tests.

D6. Sample Size Estimate. Sample size was estimated using TUG means and variances at discharge from the ongoing pilot study. In addition, literature was used to estimate long-term (> 3 months post-amputation) TUG scores for the population.^{60-62,69,70} Using 12.4 (3.9) seconds mean (SD) TUG time at rehabilitation discharge from the first 14 participants in the pilot study and 19.3 seconds as the average of TUG time reported for patients several months to years after amputation, a group difference of approximately 6.0 seconds was expected in TUG times at the 12-week time-point (primary end-point). With this group difference and an estimated SD of 6.0 (effect size = 1.0), 17 participants per group would provide 80% power to identify differences. The assumption is the EXP group will maintain or improve TUG times after the 12-week intervention and the CTL group will decline toward levels reported in the literature. A 3.4 second change in TUG represents a minimal detectable change for patients with lower limb amputation.⁶⁹

The goal is to enroll 44 participants and graduate 17 participants per group (n=34) at the 12-week test point. Based on data from the four participating hospitals, 150 patients will complete rehabilitation and achieve functional ambulation following dysvascular transtibial amputation

over the next 3 years. Based on the pilot study (Section C2), 60% of these patients are expected to meet inclusion/exclusion criteria (n = 90) and 50% of those will agree to participate (n = 45). A 20% loss to follow-up at 12 weeks (n=34) is estimated, which is twice the observed rates of studies with 12-week end-points that the PI has been involved with for other patient populations.

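### The SAP specifies maximum likelihood for 34 to 44 people with no small-sample correction; run as written, nominal 5% between-group tests run at about 6–9% and their 95% intervals are about 6–13% too narrow

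*SAP*

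**What the plan says.** The SAP is a single paragraph. It covers "Between-group differences in all outcomes at 12- and 24-week tests", to be "evaluated using maximum likelihood estimation in a multivariate repeated measures model". Each model is "controlled for baseline value of the outcome, rehabilitation clinic site (VA/non-VA), diagnosis of DM, and diagnosis of PAD". On precision it promises: "Estimated group means and within-group mean changes over time for each outcome will be reported with 95% confidence intervals". It justifies maximum likelihood by its use of all available data and by unbiasedness under missing at random. It mentions no REML, degrees-of-freedom method or reference distribution.

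Protocol section D5 (Data Analysis) describes a different primary analysis: "Group differences will be based on a linear model with TUG as the outcome", for the 12-week comparison, as a single test at alpha 0.05. It plans a mixed-effects model for 24-week outcomes. It gives no small-sample method either.

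Protocol section D6 (Sample Size Estimate) plans 44 enrolled and 34 at 12 weeks, on the basis that "an estimated SD of 6.0 (effect size = 1.0), 17 participants per group would provide 80% power".

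**The concern.** The unbiasedness that the SAP cites applies to the estimated means and differences. It does not apply to the maximum likelihood variance estimate, which makes no allowance for the mean parameters fitted. In a large trial this does not matter. With 34 to 44 people and six mean parameters per visit it does: standard errors come out too small, tests reject too often, and 95% intervals cover less than 95%.

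At stake are the 24-week and secondary results, which the SAP reports to guide further research and for which the width of the interval is much of the message. The 12-week TUG comparison is also affected if the SAP model, not the D5 model, is used for it.

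**Working it through.** **Inputs**
- Mean parameters per visit: intercept, group, baseline, site, DM, PAD, so p = 6 (SAP).
- n = 34 at 12 weeks, or 44 if everyone enrolled contributes (D6).
- Alpha 0.05 (D5), taken as two-sided; the interval level is 95% (SAP).
- SD 6.0 s and difference 6.0 s (D6).

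**The plan's own figure.** A two-sample t test with difference 6.0 and SD 6.0 has 78.1% power at 16 per group and 80.7% at 17, so D6's 17 per group is reproduced. Allowing for 20% loss, 34/0.8 = 42.5, or 43, against 44 planned. The sample size is not in question here.

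**Closed form.** With complete data, an unstructured covariance and covariates crossed with visit, the model reduces to least squares at each visit with variance RSS/n in place of RSS/(n − p). Hence:
- Standard error ratio = sqrt((n − p)/n)
- True size = P(|T| > c × ratio), with T on n − p degrees of freedom
- Relative interval width = c × ratio / t(0.975, n − p)

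Here c is 1.96 (normal reference) or t(0.975, n − p). The SAP names neither, so both are shown.

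| n | SE ratio | Reference | c × ratio | True size | Interval too narrow by |
|---|---|---|---|---|---|
| 34 | sqrt(28/34) = 0.907 | normal | 1.779 | 8.6% | 13.2% |
| 34 | 0.907 | t, 28 df | 1.859 | 7.4% | 9.3% |
| 44 | sqrt(38/44) = 0.929 | normal | 1.821 | 7.6% | 10.0% |
| 44 | 0.929 | t, 38 df | 1.881 | 6.8% | 7.1% |

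A t reference alone does not cure the problem, because the standard error is still too small. REML with a normal reference is not enough either: it gives 6.0% at n=34 and 5.7% at n=44, with intervals 4.3% and 3.2% too narrow. The residual-df variance with a t reference on n − 6 df gives 5.0%.

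**Simulation.** Two visits, unstructured covariance, 5,000 runs per scenario. Assumed, not in the documents: normal errors, visit correlation 0.6, and prevalences of 30% (site), 80% (DM) and 60% (PAD). True size of the 12-week group test:

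| Scenario | ML, normal | ML, t | REML, normal | REML, Kenward-Roger |
|---|---|---|---|---|
| n=34, covariates by visit | 8.7% | 7.5% | 6.0% | 4.8% |
| n=34, common covariates | 8.0% | 6.8% | 5.8% | 4.7% |
| n=34, common, 5 missing at 24 weeks | 8.7% | 7.5% | 6.3% | 5.3% |
| n=44, covariates by visit | 7.5% | 6.6% | 5.6% | 4.9% |
| n=44, common covariates | 7.7% | 6.7% | 5.8% | 5.2% |

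The Monte Carlo standard error is about 0.4 points. The 12-week point estimate was unbiased to within 0.01 SD. A separate simulation of 12,000 null trials per setting, under the same assumptions, gave 6.5–8.6% across both visits with no missing data. With 15% missing at week 24 it gave 6.8–9.8%; the top figure is week 24 at n=34 with covariates by visit.

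**Intervals that the SAP names.** Simulated coverage of the nominal 95% interval was:
- 12-week group mean: 91.5–93.3% (n=34) and 92.2–93.2% (n=44)
- 12-to-24-week within-group change: 90.9–94.5% (n=34) and 91.9–94.8% (n=44)

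**In TUG seconds**, taking D6's SD of 6.0 as the residual SD (an assumption). Half-width for the group difference = c × 6.0 × sqrt(2/m), with m per group, multiplied by the SE ratio for maximum likelihood:
- m=17: correct 2.048 × 6.0 × 0.343 = 4.22 s; maximum likelihood 3.66 s (normal) to 3.83 s (t)
- m=22: correct 2.024 × 6.0 × 0.3015 = 3.66 s; maximum likelihood 3.30 s (normal) to 3.40 s (t)

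**The case against.** The strongest reply is that a one-paragraph SAP is being read too literally. Maximum likelihood is invoked there mainly to explain how missing data are handled, REML is also a likelihood method, and the text does not specify a normal reference. That may be what was meant. But the SAP names maximum likelihood twice, and an analyst following it would request it. The figures are therefore conditional on that reading.

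Other points stand in part:
- **Primary test.** If D5 governs, least squares with a t test holds 5% and the primary alpha is intact. The 5% level itself comes from D5, not the SAP.
- **Which intervals.** The SAP promises intervals for group means and within-group changes, not expressly for group differences. The width figures apply to the difference. Coverage of the promised intervals is below 95% too, though for within-group change it is nearly nominal at the upper end. Change from baseline was not simulated.
- **Modelling choices.** Six parameters per visit assumes covariates crossed with visit. Counting four or five gives 6.1–8.1% size and intervals 4.7–11.5% too narrow. Missing 24-week data pushes the other way, to 9.8% and about 16%. The seconds figures probably overstate the effect, since baseline adjustment should bring the residual SD below 6.0.
- **Early-phase trial.** Secondary endpoints are openly unadjusted for multiplicity, so a per-test rate of 6–9% is a modest extra error. That waiver does not cover standard errors that are too small within each test.

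**Conclusion.** The concern holds. Full maximum likelihood run as written, without a small-sample correction, gives between-group tests with a true size of about 6–9% instead of 5% at 12 weeks, and intervals for the difference about 6–13% too narrow. Results at 24 weeks can be somewhat worse when data are missing. The closed-form figures rest on the SAP's own covariate list, complete data, normal errors and the planned numbers; they need no assumed correlation or prevalence. The simulated coverage figures do need those assumptions.

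The effect is modest and leaves point estimates and the sample size untouched. The change should be made, but the defect is not fatal. The primary alpha is at risk only if the SAP model supplies the 12-week TUG test, which the documents leave open.

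**What to change.** In the SAP, replace the maximum likelihood wording with: *restricted maximum likelihood with a small-sample degrees-of-freedom method (for example Kenward-Roger, with unstructured covariance across visits) for all tests and 95% confidence intervals.* Both parts must be named, since REML with a normal reference still ran at 5.6–6.3% in simulation. REML keeps the property that the SAP wants: it uses all available data under missing at random.

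Add one sentence stating whether the D5 linear model or the SAP model is the primary 12-week TUG test at alpha 0.05.

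The cost is one phrase, one sentence and one software option. The only downside is slightly wider intervals, which are the correct ones.
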